## 8.8 Study Exit

Once the monitoring period has ended the patient will be treated according to the hospital clinical practice. The patient will exit the study upon their discharge from the hospital. Any adverse events (as defined in section 10) observed between the end of the monitoring period and study exit are reportable (as described in section 10.2). The Study Exit eCRF will be used to document that the patient has exited from the study. The reason for study exit will be captured on the Study Exit eCRF. The date of study exit, which should correspond to the date of discharge from the hospital will also be captured here.

If the study exit was for any reason other than normal study completion, refer to section 8.12 of the CIP, for appropriate Study Exit eCRF completion.

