## 10.2 Reporting of Adverse Events

AE information will be collected throughout the study and reported to Medtronic on an AE eCRF, one for each adverse event. It is the responsibility of the investigator to identify the occurrence of adverse events to ensure that the information is accurately documented in the medical record and on the eCRFs.

Device Deficiency (DD) information will also be collected throughout the study and reported to Medtronic on a Device Deficiency eCRF. DDs require immediate reporting if they did not lead to an adverse event but could have led to a serious adverse device effect (SADE):

- if either suitable action had not been taken,
- if intervention had not been made, or
- if circumstances had been less fortunate

AE documentation will include the following information at a minimum:

- Date of event

- Time of the event
- Diagnosis and description (including confirmation of respiratory nature)
- Actions taken / treatment (including vital signs, and date and time of rescue related actions when applicable)
- Assessment of seriousness
- Relatedness to the event (including opioid therapy or device)
- Outcome or resolution and date of the resolution

For AEs that require immediate reporting, initial reporting may be done by phone, fax, e-mail, or preferably on the eCRF completing as much information as is available. The completed AE eCRF must be sent to Medtronic as soon as possible.

In case the investigator requires information from the sponsor in an emergency situation, the investigator can contact Technical Services or the Medtronic Study Manager. Contact information will be provided under separate cover.

The sponsor will ensure timely Adverse Event reporting to meet local regulatory requirements.

A list of anticipated adverse events that are expected in nature is included in Appendix A of this CIP.

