## 7.3. Center Pooling

The study will involve more than one site and a center impact on primary outcome could be investigated. A description on primary outcome by site with 95% confidence intervals for each center will be provided, as appropriate. Additional exploratory analysis on baseline characteristics could be performed to check potential difference on primary outcome among sites.

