## **7.7. Treatment Characteristics**

Extent of exposure in the population is characterized according to the duration of the study with routine monitoring.

Duration of Monitoring Exposure will be measured in minutes from the start of the monitoring through and including the time of monitoring end: Duration of monitoring exposure (minutes) = (End monitoring date/time – Start monitoring date/time). Extent of exposure will be presented in a summary table and supporting data listing.

Duration of Study Exposure will be measured in days starting from the point of enrollment (informed consent completed and inclusion/exclusion criteria confirmed per the screening evaluation) through and including the time of study exit: Duration of study exposure (days) = (Study Exit date – date of enrollment). Extent of study exposure will be presented in a summary table and supporting data listing.

Descriptive statistics will be used to summarize treatment characteristic variables for both PPS and for FAS. This will include mean, standard deviation, median, minimum, and maximum for continuous variables, and counts and percentages for categorical variables.

**Table 11 – Monitoring Exposure – FAS****Table 12 - Monitoring Exposure – PPS****Table 13 – Study Exposure – FAS****Table 14 - Study Exposure – PPS**

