## 7.9. Evaluation of Objectives

### 7.9.1. Primary Endpoint

The Primary Endpoint of the Study is to quantify the incidence of RC markers in high risk postsurgical patients, using a system comprised of two continuous monitoring devices, connected to a remote monitoring platform. The proportion and rate of “At least one RC marker” event will be calculated and reported.

The “At least one RC marker” event is defined as the occurrence of at least one of the following RC markers:

1.  $\text{SpO}_2 \leq 90\%$  for  $\geq 3$  minutes (or  $\text{SpO}_2 \leq 90\%$  for  $< 3$  min with an action taken);
2.  $\text{RR} \leq 8$  or  $\geq 22$  bpm for  $\geq 3$  minutes (or  $\text{RR} \leq 8$  or  $\geq 22$  bpm for  $< 3$  min with an action taken);
3.  $\text{EtCO}_2 \leq 15$  or  $\geq 60$  mmHg for  $\geq 3$  minutes (or  $\text{EtCO}_2 \leq 15$  or  $\geq 60$  mmHg for  $< 3$  min with an action taken);
4. Apnea episode lasting  $> 30$  seconds.

For patients monitored by PM1000N, only RC markers #1 and #2 will be considered.

RC determination will be assessed by a physician belonging to the “other” site (cross assessment by the sites). This assessment will be made by the analysis of both device and clinical data for each patient. For each patient all potential RC episodes will be derived using the Detection Tool (see Section 10.1) and will be submitted to the other site’s physician in order to adjudicate the potential RC episodes starting from episodes most likely to be RC. The adjudication will stop at the first RC occurring per patient.

The Events’ rates will be computed as (total number of “At least one RC marker” event)/(total number of time-person in PPS) and will be reported separately for each arm and phase of the study. Events’ rates will be displayed together with their 95% confidence interval (95%CI).

If the number of episode per patient result unbalanced, adjusted rates will be reported using the GEE model, together with their 95% confidence interval (95%CI).

If appropriate, also the events’ rates for each RC marker will be reported separately, for each arm and phase of the study.

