### 7.9.2. Secondary Endpoints

The secondary endpoints are:

1. To compare phases in terms of Primary endpoint incidence;
2. To compare phases in terms of respiratory and SAE incidence, number of ICU transfers and related length of stay, Code blues and RRT responses.
3. To evaluate the rate of clinical early interventions performed by nurse staff to prevent a potential AE, introducing continuous monitoring devices connected to a remote monitoring platform;
4. To evaluate the nurses’ satisfaction related to the monitoring system introducing continuous monitoring devices connected to a remote monitoring platform;
5. To establish the Predictive values of  $\text{EtCO}_2$ , RR,  $\text{SpO}_2$ , plethysmography-derived RR, IPI and EWS in respect to respiratory and other SAE.

In order to evaluate secondary **endpoints #1 and #2**, the incidence of events will be reported together with the comparison between phases, by means of the Chi-square test or Fisher exact test for extreme

proportions, as appropriate. If the monitoring/study exposure results different between phases, also the rates of events will be reported, together with the 95% Poisson Confidence Intervals. The Poisson regression model will be used to calculate the Incidence Rate ratio (IRR), with the d-scale option.

For **endpoint #3**, the rate of clinical early interventions will be calculated as (number of early interventions)/(total time-person in FAS) and it will be reported together with the 95% Poisson Confidence Interval.

Early interventions include, as defined in CRF (Monitoring Period):

1. Stimulated subject to breathe;
2. Repositioned/opened airway;
3. Held or reduced Respiratory Depressive (RD);
4. Added or increased supplemental oxygen;
5. Ventilation support;
6. Other

**Endpoint #4** will be evaluated reporting a summary of the nurses' satisfaction answers.

To identify the predictive values for EtCO2, RR, SpO2, plethysmography-derived RR, IPI and EWS, which can predict respiratory and other SAE, a sensitivity analysis will be performed (**endpoint #5**), and the following parameters will be reported, for each RC marker:

1. **Sensitivity** = 
$$\frac{(\# \text{ of clinical events "Yes" and with RC marker "Yes"})}{(\# \text{ of clinical events "Yes"})} = \frac{TP}{(TP+FN)}$$
2. **PPV** = 
$$\frac{(\# \text{ of clinical events "Yes" and with RC marker "Yes"})}{(\# \text{ of events with RC marker "Yes"})} = \frac{TP}{(TP+FP)}$$

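### Deviance scaling in SAP 7.9.2, with no stated record layout, makes the phase IRR interval too narrow when events are sparse

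*SAP*

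**What the plan says.** SAP 7.9.2 reports the incidence of endpoints #1 and #2 "together with the comparison between phases, by means of the Chi-square test or Fisher exact test", and then adds: "If the monitoring/study exposure results different between phases, also the rates of events will be reported". These rates carry 95% Poisson confidence intervals. The next sentence is the one at issue: "The Poisson regression model will be used to calculate the Incidence Rate ratio (IRR), with the d-scale option".

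Neither document gives the record layout, an offset, or a rule for deviance/df below 1. Patient-level exposure is defined in SAP 7.7 ("Duration of Study Exposure will be measured in days starting from the point of enrollment", and monitoring time in minutes). Grouped layouts are also conceivable: the primary rates are computed from totals "and will be reported separately for each arm and phase of the study", and SAP 7.3 says "A description on primary outcome by site with 95% confidence intervals for each center will be provided".

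Endpoint #1 is 0 or 1 per patient, because adjudication stops at the first confirmed RC (SAP 7.9.1). Endpoint #2 events can recur: they are "reported to Medtronic on an AE eCRF, one for each adverse event" (Protocol 10.2), and those "observed between the end of the monitoring period and study exit are reportable" (Protocol 8.8).

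**The concern.** The d-scale option multiplies the standard error of the log IRR by the square root of deviance/df. It is normally chosen to widen intervals when counts are overdispersed. When most patients have no event, however, deviance/df measures sparseness rather than dispersion and lies far below 1, so the option narrows the interval.

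Endpoint #2 covers respiratory AEs, SAEs, ICU transfers, Code blues and RRT responses. An IRR interval that wrongly excludes 1 for such events would be read as an effect of open monitoring. The phases are sequential and not randomised against each other, and no multiplicity adjustment is planned (SAP 7.5), so little else would check that reading.

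**Working it through.** **Inputs.** Phase sizes 70 and 140, planning minimum 10%, 182 evaluable (SAP 6). Monitoring 24 to 72 h (SAP 5.3). Two-sided 0.05 (SAP 7.2). Background rates from Protocol 3.1: 0.2-3.4% for respiratory failure, 2-40% for pulmonary complications, up to 37% with prolonged desaturation. The plan states no figure for the IRR or its interval, so there is none to reproduce.

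**Expected scale, one 0/1 record per patient.** With event probability p and similar exposure, expected deviance/df is about −2p ln p, while the correct variance factor is 1−p. The d-scale SE divided by the correct SE is therefore √[−2p ln p/(1−p)]. At p = 0.10: −2(0.10)ln(0.10) = 0.461, and √(0.461/0.90) = 0.72. The two factors are equal at p ≈ 0.285, so the narrowing ends near 29%.

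**Simulation.** Poisson model with phase only, log-exposure offset, Wald interval, true IRR 1, 70/140 patients. Exposure is assumed uniform 24-72 h in both phases. Entries are the share of nominal 95% intervals that exclude 1, among runs with events in both phases.

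| Event rate | −2p ln p | 1−p | d-scale | Pearson scale |
|---|---|---|---|---|
| 2% | 0.156 | 0.98 | 23% | not tabulated |
| 3.4% | 0.230 | 0.966 | 27% | 1.9% |
| 5% | 0.300 | 0.95 | 26% | 2.4% |
| 10% | 0.461 | 0.90 | 17% | 3.7% |
| 20% | 0.644 | 0.80 | 8% | 4.6% |
| 29% | 0.718 | 0.71 | 5% | 4.4% |
| 37% | 0.736 | 0.63 | 3% | 4.2% |

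Over all runs, including those with no estimable IRR, d-scale gives 16% at 2% and 25% at 3.4%. For still rarer events the IRR is seldom estimable: at 1% in 38% of runs (all-run error 6.7%), at 0.2% in 3% (0.2%). Splitting 182 in the ratio 1:2 (61/121) gives 23.7% at 3.4%, 16.4% at 10% and 7.9% at 20%.

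**Unequal exposure.** With 24-48 h against 48-72 h (assumed), d-scale gives about 21% of estimable runs at 3.4%, 15% at 10% and 8% at 20%.

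**True Poisson counts.** The effect is not an artefact of 0/1 data. At means of 0.05 and 0.10 events per patient, d-scale coverage is 72.5% and 81.7%, against 97.9% and 96.2% with the scale fixed at 1.

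**Other layouts, d-scale, at 3.4%, 5% and 10%.** Four phase-by-arm rows: 10.4%, 13.0%, 17.2%. Eight phase-by-arm-by-site rows: 2.3%, 3.7%, 7.1%. One row per phase leaves 0 df, so no scale can be estimated.

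**Hand-checkable example: 7/70 versus 7/140, equal exposure.** IRR = 0.05/0.10 = 0.50. Unscaled SE = √(1/7 + 1/7) = 0.535. Deviance = 2(7 ln 10 + 7 ln 20) = 74.2 on 208 df, scale 0.357. Pearson χ² = 63 + 133 = 196, scale 196/208 = 0.942.
- d-scale: SE 0.535 × √0.357 = 0.319, interval 0.27 to 0.93.
- Pearson: SE 0.535 × √0.942 = 0.519, interval 0.18 to 1.38.
- Fisher p = 0.24.

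**The case against.** The case on the other side has real force on scope.

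- **The output is supplementary.** This is a pilot, and the named phase comparison is Chi-square/Fisher. The SAP does not expressly promise an IRR interval. All of that stands, except that scaling changes nothing but the standard error, so naming it implies an interval or test.
- **Sparseness is partly assumed.** A reader might take 0.2-3.4% as the rate for endpoint #2 as a whole. The documents do not support that. It refers to respiratory failure only, and Protocol 3.1 also gives 2-40% for pulmonary complications, which is nearer to respiratory AEs. No rates are given for ICU transfers, Code blues or RRT responses, though these are plausibly sparse.
- **Equal exposure is not the triggering case.** Rates are added if exposure differs between phases. The unequal-exposure figures are somewhat smaller but still well above 5%.
- **The layout may be grouped.** With eight rows there is little or no inflation for sparse events. This makes the layout part of the problem: validity rests on a choice that the SAP leaves open.
- **Disagreement with Fisher is not in itself an error.** A reader might infer that the report would contradict itself. Fisher compares proportions of patients and the IRR compares rates per person-time, so they can differ legitimately when exposure differs. The example above shows the defect only because exposure there is equal.

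**Conclusion.** The point holds in limited form. With one record per patient, the d-scale interval for the phase IRR is too narrow at low event rates: about 27% false exclusion of 1 at 3.4%, 17% at 10% and 8% at 20% under equal exposure, and about 21%, 15% and 8% under the unequal exposure assumed. These are shares of estimable runs and rest on the assumed exposure distributions and the patient-level layout.

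The harm is most plausible for ICU transfers, Code blues and RRT responses. For respiratory AEs it depends on the rate. Endpoint #1 is affected at the SAP's 10% planning minimum but not near 37%, so it should not be assumed to be at fault.

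A reader might also infer that the trial's main results or its whole phase comparison are unsound. They are not affected: the primary proportions, the IRR point estimate and the Chi-square/Fisher test do not use this scale. This is a minor to moderate error in a supplementary secondary interval, worth correcting because the correction is easy.

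**What to change.** Replace the IRR sentence in SAP 7.9.2 with:

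> The IRR will be estimated by Poisson regression with one record per patient, a log-exposure offset and Pearson scaling. Where either phase has no events, the IRR will not be estimated, and counts, exposure and rates with 95% Poisson confidence intervals will be reported beside the Chi-square/Fisher test.

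Layout and scale must be stated together: Pearson scaling on four phase-by-arm rows still gives 17.5% at a 10% rate. Fixing the scale at 1 is not a safe alternative, because repeat events are possible; with overdispersed counts (assumed negative binomial, dispersion 2) its coverage is 90.4% at a mean of 0.20 and 82.8% at 0.50. Under strong overdispersion (assumed negative binomial, mean 0.1, k = 0.1), Pearson scaling gives 3.9% error, robust variance 6.3% and an exact conditional method 12.3%, so one method should be named and Pearson is the better choice.

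The cost is one sentence and one software option, with no new data. Intervals for rare events become wider and somewhat conservative (about 2% error at rates of 3.4-5%).

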#### 4.1.2. Secondary Objectives and Endpoints

The study secondary objectives are the followings:

1. To compare the two study Phases (see Section 5) in terms of primary endpoint incidence.
2. To compare the two study Phases in terms of respiratory AEs and SAE incidence, number of ICU transfers and related length of stay, Code blues and RRT responses.
3. To evaluate the impact of introducing continuous monitoring devices connected to a remote monitoring platform on the clinical workflow, defined as the rate of clinical early interventions performed by nursing staff to prevent a potential AE (e.g. patient stimulation, Jaw thrust maneuver, oxygen administration started or increased, medication change, etc.).

4. To evaluate the impact of introducing continuous monitoring devices connected to a remote monitoring platform on clinical staff workflow, defined as clinical staffs' satisfaction related to the monitoring system.
5. To characterize the predictive values of etCO2, RR, SpO2, plethysmography-derived RR, IPI and EWS in respect to respiratory AEs and other SAE.

Related secondary endpoints are:

1. Incidence of RC markers recorded by the monitoring system during each Phase.
2. Incidence of respiratory AEs and SAE, number of ICU transfers and related length of stay, Code blues and RRT responses recorded in the two study Phases.
3. Average rate of early interventions for patient will be calculated in both study Phases. In Phase I there should only be non-alarm-triggered interventions, as in clinical practice, while in Phase II there should be two sub-groups of clinical early interventions: alarm-triggered and non-alarm-triggered.
4. Clinical staff's satisfaction related to the monitoring system's introduction in their current workflow will be evaluated through a survey performed at the end of the study.
5. Sensitivity and specificity of each monitored parameter in predicting and identifying respiratory AEs and SAE will be calculated. EWS will be the only parameter not automatically collected by the monitoring system but manually collected.

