## 12.3 Analysis of clinical data

Patient demographics and baseline characteristics will be presented using appropriate summary statistics. This includes mean and standard deviation, minimum, maximum and median with the interquartile range [IQR] for continuous variables and counts and percentages for categorical variables. Summary statistics will be reported with maximum 2 decimals, as appropriate. The SAS software (SAS Institute Inc., Cary, NC, USA) will be used to perform statistical analyses. Statistical tests will be based on a two-sided significance level of 0.05. Graphical representations will be used as deemed appropriate. No adjustments for multiple comparisons or multiple look at data will be performed. Outliers and influential observations will be identified via graphical plots and according to study team decision the analysis could be repeated excluding potential outliers. In case of missing data, no imputation method will be implemented for analysis.

The Full Analysis Set (FAS) will be used for primary final analysis. Any patient who does not satisfying the inclusion/exclusion criteria will be eliminate from the FAS population. Details of endpoints analyses and additional analysis will be described in the Statistical Analysis Plan. The analyses of primary objective on the proportion of patient with at least one RC markers will be reported together with their 95% confidence intervals and separately for each arm and phase of the study (see primary endpoint definition). When comparison of clinical primary outcomes is conducted the propensity score methods could be used to control for biases and confounding which may be due to the nature of this study. The

difference between the two groups within phase and between phases within groups will be analyzed by means of unpaired t-test or Mann-Whitney test according to the normal or non-normal distribution. For one secondary outcome the logistic regression model will be used to check potential predictors. Bivariate odds ratios (ORs) and 95% confidence intervals (95% CIs) will be estimated for each predictor. A multivariate logistic regression model will be performed according to univariate model's results. Other secondary outcomes will be performed using sensitivity and specificity analysis.

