## 4.2. Secondary Objectives

The study secondary objectives are the followings:

1. To compare the two study Phases (see Section 7.1.1) in terms of primary endpoint incidence;
2. To compare the two study Phases in terms of respiratory AEs and SAE incidence, numbers of ICU transfers and related length of stay, Code blues and RRT responses;
3. To evaluate the impact of introducing continuous monitoring devices connected to a remote monitoring platform on the clinical workflow, defined as the rate of clinical early interventions performed by nurse staff to prevent a potential AE (e.g. patient stimulation, Jaw thrust maneuver, oxygen administration started or increased, medication change, etc.);
4. To evaluate the impact of introducing continuous monitoring devices connected to a remote monitoring platform on clinical staff's workflow, defined as nurses' satisfaction related to the monitoring system;
5. To characterize the predictive values of EtCO2, RR, SpO2, plethysmography-derived RR, IPI and EWS in respect to respiratory and other SAE.

Related secondary objectives are:

1. Incidence of RC markers recorded by the monitoring system during each Phase;
2. Incidence of respiratory AEs and SAE, number of ICU transfers and related length of stay, Code blues and RRT responses recorded in the two study Phases;
3. Average rate of early interventions for patient will be calculated in both study Phases. In Phase I there should only be non- alarm-triggered interventions, as in clinical practice, while in Phase II there should be two sub-groups of clinical early interventions: alarm-triggered and non- alarm-triggered;
4. Clinical staff's satisfaction related to the monitoring system's introduction in their current workflow will be evaluated through a survey performed at the end of the study;
5. Sensitivity and specificity of each monitored parameter in predicting and identifying respiratory and SAE will be calculated. EWS will be the only parameter not automatically collected by the monitoring system but manually collected.

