## 7.2. General Methodology

For FAS and PPS descriptive statistics will be used to summarize patient characteristics. This will include mean and standard deviation, minimum, maximum and median with the interquartile range [IQR] for continuous variables and counts and percentages for categorical variables. Summary statistics will be reported with maximum 2 decimals, as appropriate. Comparisons between phases have been performed using Wilcoxon's Test for continuous variables, while comparisons of categorical variables have been performed by means of the Chi-square test or Fisher exact test for extreme proportions, as appropriate. Statistical tests were based on a two-sided significance level of 0.05.

Analysis for specific objectives have been stated in the corresponding sections (7.9.1 and 7.9.2).

When comparison of clinical primary outcomes is conducted the propensity score method could be used to control for biases and confounding which may be due to the nature of this study.

It is anticipated that SAS (SAS Institute Inc., Cary, NC, USA) will be used to perform all statistical analyses. Statistical tests will be based on a two-sided significance level of 0.05.

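### The endpoint #3 intervention rate carries a plain Poisson interval that ignores variation between patients, and no Phase II/Phase I effect measure with an interval is specified

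*SAP*

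**What the plan says.** The third secondary objective, in Protocol 4.1.2 and SAP 4.2, is "To evaluate the impact of introducing continuous monitoring devices connected to a remote monitoring platform on the clinical workflow", measured by the rate of early interventions by nursing staff. SAP 4.2 adds: "Average rate of early interventions for patient will be calculated in both study Phases". It then separates the interventions by trigger: Phase I should have only those not triggered by an alarm, while "in Phase II there should be two sub-groups of clinical early interventions".

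The analysis text for this endpoint is in SAP 7.9.2, which gives the rate as "number of early interventions)/(total time-person in FAS) and it will be reported together with the 95% Poisson Confidence Interval". It mentions neither phase nor trigger, and it does not allow for several interventions in one patient.

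Two tools for extra variation appear elsewhere in the SAP:
- For endpoints #1 and #2, section 7.9.2 says: "The Poisson regression model will be used to calculate the Incidence Rate ratio (IRR), with the d-scale option".
- For the primary endpoint, section 7.9.1 says: "If the number of episode per patient result unbalanced, adjusted rates will be reported using the GEE model".

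Generic comparisons also exist. SAP 7.2 says: "Comparisons between phases have been performed using Wilcoxon's Test for continuous variables". Protocol 12.3 says the "difference between the two groups within phase and between phases within groups will be analyzed by means of unpaired t-test or Mann-Whitney test", depending on normality.

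**The concern.** A Poisson interval on a total count assumes that the variance of the count equals its mean. That fails if a few unstable patients receive many interventions and most receive none. Several features of the plan make this plausible:
- SAP 7.9.2 lists six kinds of intervention, and the example alarm response in Protocol Appendix B can lead to several actions for one alarm.
- SAP 10.1 expects several episodes close together in the same patient.
- Entry is by either of two risk scores (Protocol 7.3), so baseline risk is mixed.
- SAP 7.9.1 itself foresees uneven numbers of episodes per patient.

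The numerator for endpoint #3 is a count of repeatable actions, yet it is the endpoint left without an allowance.

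At stake are the stated precision of each phase's rate and the answer to an objective about impact. With no effect measure specified, readers would compare two Poisson intervals by eye, and both may be too narrow.

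**Working it through.** **Plan's own figure.** None. Neither document states a rate, dispersion, effect size or power for endpoint #3.

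**Inputs from the documents.** 70 patients in Phase I and 140 in Phase II (SAP 6); monitoring for 24 to 72 hours (SAP 5.3); two-sided 0.05 (SAP 7.2).

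**Assumptions.** Mean interventions per patient 0.1 to 4; gamma-distributed patient rates with coefficient of variation (CV) 1; 60 evaluable patients.

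**Step 1: dispersion.** For a gamma-Poisson count the variance-to-mean ratio is φ ≈ 1 + mean × CV². Unequal exposure raises it slightly. The Poisson interval is too short by a factor √φ, so its approximate coverage is 2Φ(1.96/√φ) − 1.

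| Mean per patient | φ at CV 1 | Approximate coverage | Simulated coverage, exact Poisson interval, n = 60, 24–72 h |
|---|---|---|---|
| 0.1–0.2 | 1.1–1.2 | 94–93% | about 95% |
| 0.5 | 1.5 | 89% | 90% |
| 1 | 2 | 83% | 84% |
| 2 | 3 | 74% | 75% |
| 4 | 5 | 62% | 61% |

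At low means the exact interval is conservative, which offsets the small loss. At CV 0.7 and mean 2, φ ≈ 1 + 2 × 0.49 = 1.98 and simulated coverage is 84%.

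**Step 2: sample size does not help.** A second simulation set φ directly, with equal exposure and 70, 140 or 210 patients (means 0.5, 1 and 2). Coverage was about 96% at φ = 1, 90% at 1.5, 85% at 2, 76% at 3 and 69% at 4, nearly the same for all three sizes.

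**Step 3: width.** Take 140 interventions in 140 patients, a rate of 1.00 per patient.
- Exact Poisson interval: 0.84 to 1.18.
- φ = 2: exp(±1.96 × √(2/140)) gives 0.79 to 1.26.
- φ = 3: exp(±1.96 × √(3/140)) gives 0.75 to 1.33.

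**Step 4: the missing rate ratio.** With one intervention per patient on average (70 and 140 events) and a common φ, SE(log ratio) = √(φ(1/70 + 1/140)). At φ = 1 this is √0.0214 = 0.146. The 95% limits are the estimate divided and multiplied by exp(1.96 × SE): 1.33 at φ = 1, 1.50 at 2, 1.64 at 3 and 1.78 at 4.

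**Step 5: the alternative interval.** An interval for the log rate that uses between-patient variance covers about 93% to 96% in the setting of Step 1. In the setting of Step 2 its lowest value is 92.6% (70 patients, mean 0.5, φ = 4). The scale matters when interventions are rare: built on the untransformed rate, the robust interval covers only about 92% at 60 patients and means of 0.1 to 0.2.

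**Step 6: the texts side by side.** SAP 4.2 and Protocol 4.1.2 fix the strata: phase, and trigger within Phase II. SAP 7.9.2 gives a formula and interval without naming the strata. By contrast, the primary endpoint text in 7.9.1 says explicitly that rates are reported by arm and phase. The rate ratio in 7.9.2 sits in the paragraph for endpoints #1 and #2 only.

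**The case against.** The strongest reply is that the shortfall is not established. Phase I alarms are silenced and screens blinded, and the sample-size section assumes that about 10% of patients have any marker. Interventions may therefore be rare, and at 0.1 to 0.2 per patient the Poisson interval performs well. This stands as a limit on the size. It does not justify the method: the low rate is also an assumption, Phase II adds alarm-triggered actions, and a log-scale robust interval costs almost nothing when φ = 1.

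It can also be said that this is a descriptive secondary rate in a pilot. That limits the priority of the change but is no reason to leave the interval as it is.

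Three stronger readings are tempting, and the documents do not support them:
- **A reader might infer that only one pooled rate is planned, so objective 3 goes unanswered.** SAP 4.2 and Protocol 4.1.2 commit to a rate in both phases with the trigger split. Section 7.9.2 is silent on phases and does not say the rate is pooled.
- **A reader might infer an inflated false-positive rate for the phase comparison.** No unscaled Poisson phase test is specified for endpoint #3. The generic t-, Wilcoxon and Mann-Whitney tests, if applied to it, take the patient as the unit. In a simulated check (70 versus 140 patients, mean 1, CV 1, equal exposure), Mann-Whitney rejected in 5.2% of null trials.
- **A reader might infer that the rate must also be split by device.** SAP 4.2 does not ask for this for endpoint #3, and SAP 7.1.1 says arms will not be compared.

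**Conclusion.** The point holds in a limited form. The stated interval has no allowance for between-patient variation and is too narrow if per-patient counts are overdispersed, which the plan's own features make plausible. On the assumed grid at CV 1, coverage runs from about 95% when interventions are rare to 61% at four per patient. The documents do not say where in that range the trial lies, so the shortfall may be negligible or large.

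On phases, the gap is one of carry-through. Phase-specific rates are planned, but the analysis section does not repeat the strata, and the generic tests give at most a p-value. What is missing is a Phase II/Phase I effect measure with an interval. This should be corrected before analysis; it does not threaten the primary result.

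**What to change.** In SAP 7.9.2, for endpoint #3:
1. Apply the rate formula by phase, with Phase II split into alarm-triggered and non-alarm-triggered interventions, as SAP 4.2 already requires.
2. Replace the plain Poisson interval with one clustered on the patient: GEE with robust variance or a negative binomial model, each with a log monitored-time offset, or a patient-level bootstrap. Form model-based intervals on the log scale.
3. Extend the Phase II/Phase I incidence rate ratio to endpoint #3, with its 95% interval from the same variance.
4. State that person-time is monitored time, since SAP 7.7 defines both monitoring and study exposure. Reconcile this with the per-patient average in SAP 4.2.

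No new data are needed: interventions (alarm-related or not) and monitoring duration are already collected (Protocol Table 2, SAP Table 1). The cost is SAP wording, a few lines of code and somewhat wider intervals.
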